5.15.4. Non-IMP Medications and Non-Drug Therapy/Procedures

The use of non-IMP medications will be coded using the World Health Organization (WHO) drug dictionary (WHODrug) ([Version: Global B3 September 2019 or later](#)). Concomitant medications, with start date on or after the date of the first IMP through the last IMP dose date, will be summarized by treatment group, frequency of drug classification, and generic drug name. Incidence of dosage adjustment of levodopa (L-Dopa) or equivalent during treatment period, prohibited by the protocol, for duration longer than one week will be summarized. Medications with start date after the last dose of IMP through the end of protocol-defined reporting period, will also be summarized. All prior, concomitant, and post IMP medications will be presented in a data listing.

The use of non-drug therapy/procedures will be coded using MedDRA Version 26.1 or higher. Concomitant and post-IMP non-drug therapy/procedures will be summarized by treatment group, frequency of system organ class and preferred term. All prior, concomitant, and post-IMP non-drug therapy/procedures will be presented in a data listing.

5.15.5. Clinical Laboratory Assessments

Descriptive summaries of selected (quantitative) clinical laboratory results will be presented by treatment group and study visit. Laboratory values outside the normal range for each systematically collected hematology, blood chemistry, and urinalysis parameter will be identified. Each subject's hematology, blood chemistry, and quantitative urinalysis values will be flagged as "low" (below the lower limit of normal/LLN), "normal" (within the normal range), or "high" (above the upper limit of normal/ULN) relative to the normal ranges of the central laboratory. Each subject's qualitative urinalysis results will be flagged as "normal" or "abnormal." In addition, toxicity grade will be determined for laboratory tests with toxicity grade based on Common Terminology Criteria for Adverse Events (CTCAE) Version 5.0 with implementation specifications in [Section 9.8](#). The result of each laboratory test for individual

subjects will be presented in a listing with the normal range defined by the central laboratory, the status relative to the normal range, and the CTCAE toxicity grade.

Shift table will be used to summarize shifts from baseline toxicity grades to greatest (worst) treatment-emergent laboratory toxicity grades based on CTCAE criteria. For hematology and, blood chemistry, and quantitative urinalysis parameters that no CTCAE toxicity grade was defined, a shift table for each laboratory test will be based on the shift from baseline high/normal/low status to the status of the maximum post-baseline value and the minimum post-baseline value (including test results from unscheduled visits, if any). Similarly, for qualitative urinalysis parameters, shifts from baseline normal/abnormal status to the worst post-baseline status will be summarized.

The number and percentage of subjects who have post-baseline elevations in liver transaminase (alanine aminotransferase [ALT] or aspartate aminotransferase [AST]) or bilirubin abnormalities in relation to fold above the upper limit of normal will be summarized according to the Food and Drug Administration's Premarketing Clinical Evaluation on Drug-Induced Liver Injury Guidance for Industry ([FDA 2009](#)). Abnormal hepatic laboratory values will be categorized and evaluated for any occurrence among all post-baseline assessments (where “and” in the bulleted list below indicates elevations occurring at the same visit). Within each laboratory parameter grouping, a subject may be counted once per elevation criteria using the worst-case result. That is, a subject with a worst case ALT elevation $> 5 \times$ the ULN would be counted once in the ALT $> 3 \times$ ULN category and once in the ALT $> 5 \times$ ULN category, regardless of how many ALT elevations the subject had that met the $> 3 \times$ ULN and $> 5 \times$ ULN elevation criteria.

- ALT and/or AST $> 3 \times$ ULN and total bilirubin > 1.5 or $2 \times$ ULN
- AST $> 3, 5, 10, 20 \times$ ULN
- ALT $> 3, 5, 10, 20 \times$ ULN
- Total bilirubin $> 1.5, 2 \times$ ULN
- Alkaline phosphatase (ALP) $> 1.5 \times$ ULN

In addition, a Hy’s law plot, a shift plot showing liver safety panel tests over time (baseline vs. post-baseline), and distribution plots of ALT, AST, ALP, and bilirubin over time will be produced to aid identification of any potential cases ([Merz M. et. al. 2014](#)). The plots to be included are the scatter plot of maximum transaminase versus maximum bilirubin, the liver test safety panel over time, and the distribution of ALT by time. The distribution plots for AST, ALP, and bilirubin will use the same format as used for ALT.

5.15.6. Vital Signs

Vital signs include systolic and diastolic blood pressures, heart rate, and body temperature. Supine (after 5 minutes of rest) and standing (2 minutes after rising from supine to standing) measurements will be obtained for blood pressure and heart rate. Duplicate readings of supine blood pressure and heart rate will be taken. The duplicate values will be individually recorded, and the values will be averaged by the sponsor for the time point assessment. Orthostatic changes

will be derived using standing and supine values. Body temperature will be obtained once, at the time of the first blood pressure measurement.

5.15.6.1. Blood Pressure and Heart Rate

Blood pressure and heart rate measurements and corresponding changes from baseline will be summarized by treatment group, position (if applicable), and visit using descriptive statistics.

Number and percent of subjects with at least one of the out-of-range value in blood pressure and heart rate will be summarized by treatment group based on the following criteria:

Supine Systolic Blood Pressure (mmHg)

- < 80 mmHg
- < 90 mmHg
- > 140 mmHg
- > 160 mmHg
- > 200 mmHg

Change from Baseline in Supine Systolic Blood Pressure (mmHg)

- < -20 mmHg
- < -10 mmHg
- > 10 mmHg
- > 20 mmHg

Orthostatic Systolic Blood Pressure (mmHg)

- ≥ 20 mmHg decrease upon standing compared with supine position
- ≥ 20 mmHg increase upon standing compared with supine position

Supine Diastolic Blood Pressure (mmHg)

- < 50 mmHg
- > 90 mmHg
- > 100 mmHg
- > 120 mmHg

Change from Baseline in Supine Diastolic Blood Pressure (mmHg)

- < -15 mmHg
- < -10 mmHg
- > 10 mmHg
- > 25 mmHg

Orthostatic Diastolic Blood Pressure (mmHg)

- ≥ 10 mmHg decrease upon standing compared with supine position
- ≥ 10 mmHg increase upon standing compared with supine position

Supine Heart Rate (beats/min)

- < 50 bpm
- < 60 bpm
- > 100 bpm and ≤ 120 bpm
- > 120 bpm

The number of percentage of the out-of-range values will also be summarized by treatment phase (titration, dose adjustment and maintenance phase). For supine measurements, the average of the duplicate will be used to determine out-of-range status, unless in isolated cases where only a single measurement was taken.

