The safety results across all clinical trials demonstrate that tavapadon was generally well tolerated up to a titrated dose of 15 mg QD in subjects with PD, either as monotherapy (early PD) or as adjunctive treatment with a stable dose of L-Dopa (advanced PD). A dose-dependent increase in the frequencies of nausea and headache was observed across all trials. Nausea, vomiting, dyskinesia, fall, fatigue, sleep disorder, and tremors were the most common AEs leading to discontinuation of tavapadon. The appearance of nausea, orthostatic blood pressure changes, and fatigue is often related to the speed of titration with dopamine receptor agonists (historically with D2 agents) and may be mitigated by a slower titration method.

No notable differences in laboratory abnormalities, electrocardiogram (ECG) parameters, or suicidality assessments were observed between tavapadon and placebo. Multidose cohorts in Phase 1 trials in healthy volunteers and subjects with PD (including subjects with PD who were treated at doses of up to 25 mg QD of tavapadon) did not suggest that tavapadon prolonged the QT interval corrected for heart rate by Fridericia's formula (QTcF). Trials of longer treatment duration suggest a tavapadon dose-related decrease from baseline in systolic and/or diastolic parameters, with some cases of asymptomatic hypotension. This finding is common with dopamine D2 agonists and is prevalent in the population of patients with PD whether treatment naïve or treated with L-Dopa.

Taken together, the current data suggest an appropriate benefit-risk ratio for further evaluation of tavapadon in Phase 3 clinical trials at doses up to 15 mg QD. Additional information about the known and expected benefits, risks, and AEs of tavapadon is provided in the Investigator's Brochure.

In response to the COVID-19 pandemic, Cerevel has performed a risk assessment of this trial and the investigator of each individual trial site and has implemented measures throughout the protocol, which prioritizes trial participant safety and data validity.

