14.	Subjects with a history of myocardial infarction with residual atrial, nodal, or ventricular arrhythmias that are not controlled with medical and/or surgical intervention; second- or third-degree atrioventricular block; sick sinus syndrome; severe or unstable angina; or congestive heart failure within the last 12 months. A recent (≤ 12 months) history of myocardial infarction with secondary arrhythmias is exclusionary regardless of the therapeutic control.
15.	Subjects with a history of neuroleptic malignant syndrome.
16.	Female subjects who are breastfeeding and/or who have a positive pregnancy test result prior to receiving IMP.

Prior or Concomitant Medications

17.	Subjects who are currently receiving moderate or strong CYP3A4 inducers or CYP3A4 inhibitors (except for topical administration).
18.	Subjects with a positive urine drug screen for illicit drugs are excluded and may not be retested or rescreened. Subjects with a positive urine drug screen resulting from use of marijuana (any THC-containing product), prescription, or over-the-counter medications or products that, in the investigator's documented opinion, do not signal a clinical condition that would impact the safety of the subject or interpretation of the trial results may continue evaluation for the trial following consultation and approval by the medical monitor.
19.	Subjects who are using prohibited medications prior to randomization (as listed in Table 6) or who would be likely to require the use of prohibited concomitant medications during the trial (as listed in Table 7).

Screening Assessments

20.	Subjects with a MoCA score <26 .
21.	Subjects with a supine blood pressure ≥ 160 mmHg (systolic) or ≥ 100 mmHg (diastolic) at screening. The average of two supine measurements will be used to assess eligibility.
22.	Subjects with clinically significant orthostatic hypotension (eg, syncope).

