5.15.7. Electrocardiograms (ECGs)

Single or triplicate 12 lead ECGs will be obtained during the trial. All ECG recordings will be obtained after the subject has been supine and at rest for at least 5 minutes. A triplicate set of ECGs is 3 consecutive ECGs collected 1 to 2 minutes apart over a 5 minute period. Any values taken in triplicate will be averaged for analysis. ECGs and corresponding changes from baseline will be summarized by treatment group and visit using descriptive statistics.

The number and percentage of subjects who experience any post-baseline occurrence of potentially clinically significant corrected QT values using Fridericia's method (QTcF) will be summarized by treatment group. These presentations will include QTcF values > 450 to ≤ 480 , > 480 to ≤ 500 , and > 500 msec; or changes of > 30 to ≤ 60 or > 60 msec (FDA, 2005). For this

categorization, the average of triplicate values will be utilized rather than the individual values comprising the triplicate measurement.

Additionally, a distribution plot of QTcF over time will be produced aid identification of any possible time trend and outliers.

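### SAP 5.15.6.1 does not limit its orthostatic and absolute supine blood pressure counts to post-baseline values or separate pre-existing cases, and the orthostatic criteria have no baseline-referenced count

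*SAP*

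**What the plan says.** SAP 5.15.6.1 plans three kinds of blood pressure summary.

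- **Continuous:** "Blood pressure and heart rate measurements and corresponding changes from baseline will be summarized by treatment group, position (if applicable), and visit".
- **Threshold counts:** "Number and percent of subjects with at least one of the out-of-range value in blood pressure and heart rate will be summarized by treatment group". The list holds absolute supine limits (systolic below 80 or 90 and above 140, 160 or 200 mmHg; diastolic below 50 and above 90, 100 or 120 mmHg). It also holds categories of "Change from Baseline in Supine Systolic Blood Pressure (mmHg"), a parallel set for supine diastolic pressure, and orthostatic criteria. The systolic orthostatic criterion for a fall is at least a "20 mmHg decrease upon standing compared with supine position"; the diastolic one is 10 mmHg, and increases on standing are listed too.
- **By phase:** the out-of-range counts are repeated for titration, dose adjustment and maintenance.

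Protocol 2.3 gives the background. "Trials of longer treatment duration suggest a tavapadon dose-related decrease from baseline in systolic and/or diastolic parameters", with some asymptomatic hypotension, and the finding "is prevalent in the population of patients with PD whether treatment naïve or treated with L-Dopa". The relevant eligibility rule, exclusion 22 in Protocol 5.2, removes "Subjects with clinically significant orthostatic hypotension (eg, syncope"). Exclusion 21 sets only upper limits on supine pressure.

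Elsewhere the SAP is more explicit about timing. The QTcF table (SAP 5.15.7) counts subjects "who experience any post-baseline occurrence of potentially clinically significant corrected QT values", the liver counts in SAP 5.15.5 are limited to post-baseline assessments, and the laboratory section uses shift tables from baseline.

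**The concern.** An orthostatic drop is a difference within one visit, so the criterion carries no information about the subject's state before treatment. As worded, a subject who shows the drop at screening or on Day 1 before dosing already has a qualifying value. Even if only later readings were used, a subject with a standing tendency to drop would probably qualify at one of the nine post-baseline visits. Such subjects enter the numerator in both arms whatever the drug does.

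The protocol gives this parameter weight. Its rationale lists dose-limiting hypotension first among the effects tavapadon is meant to minimise, and Protocol 2.3 reports a suggested pressure decrease. A count swollen by pre-existing cases makes the arms look more alike than they are for new cases. For a safety signal that is the less cautious direction. A reader of the orthostatic rows could not tell new cases from old ones.

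**Working it through.** **Inputs from the documents.** Neither document gives a blood pressure rate, a baseline prevalence or a new-onset rate, so there is no plan figure on this point to reproduce. The one design figure used is 184 subjects per arm, and it is consistent with the SAP's inputs (difference 1 hour, SD 2.5, two-sided alpha 0.049, power 90%, dropout 27%):

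- n per arm = 2 × (1.969 + 1.282)² × 2.5² / 1² = 132.1, rounded up to 133.
- Total = 266 / 0.73 = 364.4, rounded up to 365, against 368 stated.
- With 135 completers per arm, noncentral-t power is 90.4%, as in SAP Table 5.

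**Assumptions, not from the documents.**

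- b, the share meeting the criterion at baseline, equal in both arms by randomisation: 10% to 40%.
- r, the chance that such a subject is counted, equal in both arms: 1. This is exact if pre-dose readings qualify, as the wording allows.
- New onset among the rest: 10% on placebo (qP), 20% on tavapadon (qT).

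**Formulas.** All-subject rate = b·r + (1 − b)·q. The difference between arms is therefore (1 − b)(qT − qP), and the ratio is [b·r + (1 − b)qT] / [b·r + (1 − b)qP].

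| b | Placebo | Tavapadon | Difference | Ratio | Baseline-negative per arm |
|---|---|---|---|---|---|
| 0% | 10% | 20% | 10 points | 2.00 | 184 |
| 10% | 0.10 + 0.90 × 0.10 = 19% | 0.10 + 0.90 × 0.20 = 28% | 9 points | 1.47 | 166 |
| 20% | 0.20 + 0.80 × 0.10 = 28% | 0.20 + 0.80 × 0.20 = 36% | 8 points | 1.29 | 147 |
| 30% | 0.30 + 0.70 × 0.10 = 37% | 0.30 + 0.70 × 0.20 = 44% | 7 points | 1.19 | 129 |
| 40% | 0.40 + 0.60 × 0.10 = 46% | 0.40 + 0.60 × 0.20 = 52% | 6 points | 1.13 | 110 |

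Among baseline-negative subjects the comparison stays at 20% against 10% throughout.

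**Sensitivity.**

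- With r = 0.8 the differences are unchanged and the ratios are 1.53, 1.33, 1.23 and 1.16 at b = 10%, 20%, 30% and 40%.
- With new onset of 30% against 20%, a ratio of 1.50 falls to 1.32 at b = 10% and 1.12 at b = 40%.
- With 12% against 5%, a ratio of 2.40 falls to 1.43 and 1.10.

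**Would post-baseline wording be enough?** Vital signs are scheduled at nine post-baseline visits (Weeks 2, 5, 8, 11, 14, 18, 22, 26 and 27). If a baseline-positive subject had an assumed independent 30% chance of showing the drop at each visit, the chance of at least one is 1 − 0.7⁹ = 96%. The wording change removes pre-dose readings but leaves nearly all pre-existing cases in the count, so a baseline-referenced row is needed as well.

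**The case against.** The case on the other side is substantial.

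- **Baseline is not ignored across the section.** Supine systolic and diastolic pressure have change-from-baseline categories, and these count the kind of decrease Protocol 2.3 describes. Mean changes from baseline are also given by position and visit, so standing pressure is covered. This stands and confines the point. Mean changes, however, do not show how many subjects newly cross an orthostatic threshold.
- **Counts are repeated by phase.** Dose adjustment and maintenance counts cannot include a pre-dose reading. True, but they still include subjects who were positive before dosing.
- **Clinically important cases have another route.** Protocol 10.3.1 makes clinically significant vital-sign abnormalities adverse events, including worsening from baseline. Occurrences before dosing go to medical history, and SAP 5.15.1 tabulates treatment-emergent events by phase and by dose at onset. This stands for cases an investigator judges significant; the threshold table exists for the others.
- **Exclusion 26 also applies.** It removes abnormal vital signs unless they are judged not medically significant. That narrows entry but still admits an asymptomatic drop.
- **The comparison with other tables goes only so far.** The QTcF and liver counts are post-baseline, but they are not limited to subjects below the threshold at baseline. They support the wording change only. The laboratory shift tables are the nearer precedent for a baseline-referenced display.
- **The tables are descriptive.** Protocol 9.4.2 plans no test, so no formal conclusion is affected.

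A reader might also infer that the plan dilutes a known dose-related orthostatic effect. The documents do not support that. Protocol 2.3 says only that longer trials suggest a systolic and/or diastolic decrease. Its prevalence remark refers to that finding, and it mentions orthostatic change only in connection with titration speed for dopamine agonists generally.

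**Conclusion.** The point holds in a limited form. The orthostatic and absolute supine threshold counts are not restricted to post-baseline values and do not separate pre-existing cases. Only the orthostatic criteria lack any baseline-referenced count. Since asymptomatic drops are not excluded at entry, the arm difference in these rows shrinks by the factor (1 − b) when pre-existing cases are counted equally in both arms.

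The size cannot be established, because b, persistence and onset rates are all absent from the documents. The fall from a ratio of 2.0 to between 1.47 and 1.13 illustrates the mechanism on assumed inputs; it is not an estimate. On the absolute scale the loss is smaller, from 10 points to between 9 and 6.

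It would be wrong to read this as bias toward one arm, since randomisation is expected to balance pre-existing cases. It would also be wrong to conclude that hypotension goes unassessed or that a hypothesis test is compromised. The matter is a less informative descriptive safety table, on a parameter the protocol itself highlights, and it can be improved with data already scheduled.

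**What to change.** In SAP 5.15.6.1:

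1. State that the out-of-range counts use post-baseline values.
2. For the orthostatic criteria and the low supine thresholds, add one of two displays, overall and by treatment phase. The first is a shift from baseline status to worst post-baseline status. The second is the number and percentage with a post-baseline occurrence among subjects who did not meet the criterion at baseline. Take baseline from SAP 4.1.7 and orthostatic change from SAP 4.1.9.
3. Keep the planned all-subject rows.

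The cost is SAP wording, one baseline flag per criterion and a few table rows. Supine and standing readings at screening and baseline are already scheduled, so no new data are needed. There are two drawbacks. The added rows lose the baseline-positive share, which is not negligible if prevalence is high: on the illustration, 184 per arm becomes 166 at 10% and 110 at 40%. Baseline orthostatic status would also rest on a single standing reading, so some subjects will be misclassified. The shift table keeps every subject with a baseline and a post-baseline value in view, so it avoids the first drawback but not the second.

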5.15.6.2. Body Weight

Body weight measurements at baseline and at the end of treatment with corresponding changes from baseline will be summarized by treatment group using descriptive statistics.

Number and percent of subjects with out-of-range body weight changes will be summarized based on the following criteria:

- Decrease from Baseline 7% or more (i.e. change from baseline $\leq -7\%$)
- Increase from baseline 7% or more (i.e. change from baseline $\geq 7\%$)

5.15.6.3. Temperature

Number and percent of subjects with out-of-range temperature will be summarized based on the following criteria:

- >38.0 °C
- <36.0 °C

5.15.7. Electrocardiograms (ECGs)

Single or triplicate 12 lead ECGs will be obtained during the trial. All ECG recordings will be obtained after the subject has been supine and at rest for at least 5 minutes. A triplicate set of ECGs is 3 consecutive ECGs collected 1 to 2 minutes apart over a 5 minute period. Any values taken in triplicate will be averaged for analysis. ECGs and corresponding changes from baseline will be summarized by treatment group and visit using descriptive statistics.

The number and percentage of subjects who experience any post-baseline occurrence of potentially clinically significant corrected QT values using Fridericia's method (QTcF) will be summarized by treatment group. These presentations will include QTcF values > 450 to ≤ 480 , > 480 to ≤ 500 , and > 500 msec; or changes of > 30 to ≤ 60 or > 60 msec (FDA, 2005). For this

categorization, the average of triplicate values will be utilized rather than the individual values comprising the triplicate measurement.

Additionally, a distribution plot of QTcF over time will be produced aid identification of any possible time trend and outliers.

5.15.8. Physical and Neurological Examinations

Physical and Neurological examination data will be listed.

5.15.9. Columbia-Suicide Severity Rating Scale (C-SSRS)

The maximum post-baseline results from the C-SSRS will be summarized. The maximum of each subscale (suicidal ideation [Categories 1-5], suicidal behavior [Categories 6-10], suicidal ideation or behavior [Categories 1-10], and self-injurious behavior without suicidal intent) will be presented. The number of patients with suicide-related treatment-emergent events, treatment-emergent suicidal ideation, and suicidal behavior, based on a comparison of the C-SSRS at baseline and/or previous lifetime experience to maximum C-SSRS scores across all post-baseline assessments will be provided. All C-SSRS elements will be reflected in a listing.

